### **3.2.2 Medical history and prior procedures**

The eCRF collects any relevant medical histories and prior procedures. Medical history and prior procedures are coded in MedDRA version 23.0 or higher.

The procedures are classified as prior as below:

The imputation method described in section 3.1.1.5 is used in case the procedure end date is partially missing. The imputation method described in section 3.1.1.1 is used in case the first dose of IP date and time are missing or partially missing.

After the end date imputation, the procedures will be classified as either prior or concomitant (but not both) according to the end date. Prior procedure is defined as any procedure with an end date prior to the first dose of IP (exclusive). Concomitant procedure is defined as any procedure with an end date on or after the first dose of study drug. Procedures with completely missing end date are classified as concomitant.

### **3.2.3 Nicotine and alcohol use**

Nicotine and alcohol use (never-current-former) are collected at screening.

## **3.3 Efficacy, safety and exploratory variables**

The primary efficacy endpoint of the study is

1. the change from baseline in log-transformed dLDL-C compared with placebo descriptively for all visits and within a statistical model at the week 12.

The secondary efficacy endpoints of the study are:

2. the change from baseline in log transformed PCSK9 compared with placebo descriptively for all visits and within a statistical model at the week 12
3. the percent change from baseline in dLDL-C compared with placebo descriptively for all visits and within a statistical model at the week 12.
4. Correlation of LDL-C Friedewald and LDL-C Martin-Hopkins with dLDL-C
5. Level of other lipid parameters compared with placebo descriptively for all visits and within a statistical model at the week 12. Other lipid parameters include:
  - TC
  - HDL-C
  - Non-HDL-C
  - VLDL-C
  - ApoA1
  - ApoB

- Lp(a)
  - Triglycerides
  - Remnants cholesterol
6. PK parameters (to be reported in a separate report)
  7. Development of ADA and immunogenicity titre during the on-treatment and follow-up analysis phases

The safety endpoints of the study are:

8. AE
9. Vital signs
10. ECG
11. Safety clinical laboratory parameters

The exploratory endpoint of the study is:

12. Lipoprotein profile

Efficacy, safety, and exploratory endpoints are collected as reported in section 1.2.

### **3.3.1 Primary endpoint**

#### **3.3.1.1 Change from baseline in log-transformed dLDL-C**

dLDL-C is assessed in a central laboratory. LDL-C is assigned to the analysis visits and analysis phase as described in section 3.1.2 and 3.1.3. Measurements with missing or partial missing dates are not assigned to any analysis visit / analysis phase. dLDL-C below the LLOQ for which the exact value cannot be determined, will be replaced with the LLOQ divided by the squared root of 2.

After the LLOQ replacement, change from baseline of the log-transformed variable is calculated as the visit value in natural logarithm minus the baseline value in natural logarithm. The relative change from baseline is calculated back transforming the change from baseline of the log-transformed variable.

### **3.3.2 Secondary efficacy endpoints**

#### **3.3.2.1 Change from baseline in natural logarithm transformed PCSK9**

PCSK9 is assessed in a central laboratory. PCSK9 is assigned to the analysis visits and analysis phases as described in sections 3.1.2 and 3.1.3. Measurements with missing or partial missing dates are not assigned to any analysis visit / analysis phase. PCSK9 below the LLOQ for which the exact value cannot be determined, will be replaced with the LLOQ divided by the squared root of 2.

After the LLOQ replacement, change from baseline of the log-transformed variable is calculated as the visit value in natural logarithm minus the baseline value in natural logarithm. The relative

change from baseline is calculated back transforming the change from baseline of the log-transformed variable. Percent change from baseline is also calculated as the visit value minus the baseline value divided by the baseline value \*100.

### **3.3.2.2 Percent change from baseline in LDL-C**

dLDL-C is assessed in a central laboratory. dLDL-C is assigned to the analysis visits and analysis phases as described in sections 3.1.2 and 3.1.3. Measurements with missing or partial missing dates are not assigned to any analysis visit / analysis phase. dLDL-C below the LLOQ for which the exact value cannot be determined, will be replaced with the LLOQ divided by the squared root of 2.

After the LLOQ replacement, percent change from baseline is calculated as the visit value minus the baseline value divided by the baseline value \*100.

### **3.3.2.3 LDL-C Friedewald and LDL-C Martin-Hopkins**

LDL-C Friedewald and LDL-C Martin-Hopkins are also derived in a central laboratory. LDL-C Friedewald and LDL-C Martin-Hopkins are assigned to the analysis visits and analysis phase as described in section 3.1.2 and 3.1.3. Measurements with missing or partial missing dates are not assigned to any analysis visit / analysis phase.

### **3.3.2.4 Level of other lipid parameters**

Other lipid parameters include:

- TC
- HDL-C
- Non-HDL-C
- VLDL-C
- ApoA1
- ApoB
- Lp(a)
- Triglycerides
- Remnants cholesterol

Lipid parameters are assessed in a central laboratory. Lipid parameters are assigned to the analysis visits and analysis phases as described in sections 3.1.2 and 3.1.3. Measurements with missing or partial missing dates are not assigned to any analysis visit / analysis phase. Lipid parameters below the LLOQ for which the exact value cannot be determined, will be replaced with the LLOQ divided by the squared root of 2.

After the LLOQ replacement, change from baseline of the log-transformed variable is calculated as the visit value in natural logarithm minus the baseline value in natural logarithm. The relative change from baseline is calculated back transforming the change from baseline of the log-transformed variable. Percent change from baseline is also calculated for all variables as the visit value minus the baseline value divided by the baseline value \*100.

### **3.3.2.5 Pharmacokinetic parameters**

PK concentrations are tested in a central external laboratory as per scheduled timepoints.

PK concentrations are assigned to the analysis visits as described in section 3.1.2. Measurements with missing or partial missing dates are not assigned to any analysis visit. PK concentrations below the LLOQ for which the exact value cannot be determined, will be replaced with the LLOQ.

PK parameters are not derived and analysed within this SAP. Details on pharmacokinetic parameters are provided in an additional bioanalytical report prepared by a dedicated pharmacometrics support group at AstraZeneca.

### **3.3.2.6 Immunogenicity**

Immunogenicity parameters are:

- ADA
- Immunogenicity titre

These parameters are tested in an external laboratory. A validated screening assay will be used to determine ADA positive samples. Any positive samples will be tested in a confirmatory assay whereby the specificity of the ADA response will be confirmed as either positive or negative with respect to AZD8233. Titre evaluation are performed on samples that are confirmed positive for ADA.

All these parameters are assigned to the analysis visits and to the analysis phases as described in section 3.1.2 and in section 3.1.3. Measurements with missing or partial missing dates are not assigned to any analysis visit / analysis phase. ADA confirmed positive results with titre lower than the MRD (<50) will be replaced with titre =50 for the statistical analysis.

The study day of ADA measurement is calculated as the date of the ADA sample collection – the date of first IP +1 for ADA sample collected on or after the day of first IP and as the date of the ADA sample collection – the date of first IP for ADA sample collected before the day of first IP.

## **3.3.3 Safety endpoint**

### **3.3.3.1 Adverse events**

An adverse event is the development of any untoward medical occurrence in a subject or clinical study subject administered a medicinal product and which does not necessarily have a causal relationship with this treatment. An AE can therefore be any unfavourable and unintended sign (e.g., an abnormal laboratory finding), symptom (e.g., nausea, chest pain), or disease temporally associated with the use of a medicinal product, whether or not considered related to the medicinal product. The term AE is used to include both serious and non-serious AEs and can include a deterioration of a pre-existing medical occurrence. An AE may occur at any time, including run-in or washout periods, even if no study treatment has been administered. SAEs will be collected from time of signature of informed consent, throughout the treatment period

and including the follow-up period. All non-serious AEs will be recorded from time of first dose of IP, throughout the treatment period and including the follow-up period. Adverse events (AEs) will be coded with MedDRA version 23.0 or higher. For any additional details on AE reporting please refer to the study protocol.

After start and end date imputation as per section 3.1.1 the AEs are assigned to the study phases described in section 3.1.3, based on the AE start date and time as follows:

If both the start date and start time of an AE are known, then:

- If the AE start datetime is before the first dose of IP datetime, then the AE is assigned to the pre-treatment phase.
- If the AE start datetime is on or after the first dose of IP datetime, then the AE is assigned to the on-treatment phase,

If only the start date of an AE is known, and the start time of the AE is unknown, then:

- If the AE start date is before the first dose of IP date, then the AE is assigned to the pre-treatment phase,
- If the AE start date is on or after the first dose of IP date then the AE is assigned to the on-treatment phase,

If the start date of an AE is completely missing, the AE is assigned as follow:

- If the AE end date is known and is before the first dose of IP date, then the AE is assigned to the pre-treatment phase,
- If the AE end date is completely missing or if the AE end date is on or after the first dose of IP date no assignment can be done.

All the AE in the on-treatment phase are considered TEAEs.

The study day of AE is calculated as the start date of the AE – date of first IP +1 for AE started on or after the day of first IP and as start date of the AE – date of first IP for AE started before the day of first IP. Imputed dates should not be used. If one of the dates is missing or partially missing, the study day of the start of the AE is set to missing.

The duration of AE is calculated as the end date of the AE – start date of the AE +1. Duration is calculated for complete dates only. Imputed dates should not be used. If one of the dates is missing or partially missing, the duration is missing.

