#### 8.3.1 Time Period and Frequency for Collecting AE and SAE Information

Adverse events will be collected from time of first dose throughout the treatment period and including the follow-up period.

Serious adverse events will be recorded from the time of signing of the ICF.

If the Investigator becomes aware of an SAE with a suspected causal relationship to the study intervention that occurs after the end of the clinical study in a participant treated by him or her, the Investigator shall, without undue delay, report the SAE to the sponsor.

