### **Adverse event variables**

The following variables will be collected for each AE:

- AE (verbatim)
- The date and time when the AE started and stopped
- Maximum intensity
- Whether the AE is serious or not
- Investigator causality rating against the study intervention (yes or no)
- Action taken with regard to the study intervention
- AE caused participant's withdrawal from study (yes or no)
- Outcome

In addition, the following variables will be collected for SAEs:

- Date AE met criteria for serious AE
- Date Investigator became aware of serious AE
- AE is serious due to
- Date of hospitalisation
- Date of discharge
- Probable cause of death
- Date of death
- Autopsy performed
- Causality assessment in relation to Study procedure(s)
- Causality assessment to other medication

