### 3.1.1.4 Imputation of AE start date

Before to proceed with the AE start date imputation, the first dose of IP and the AE end date are imputed as described in the previous section.

Only partial AE start dates are imputed; Dates which are completely missing are not imputed. Partial dates are imputed as described below:

If the day is missing and the month and/or the year is different from the month and year of the first dose of IP, assume 01-*MMM*-*YYYY*. If the month and year are the same as the first dose of IP month and year and the end date is on or after (including ongoing / missing) the first dose of IP, then assume the date of the first dose of IP. If the month and year are the same as the first dose of IP month and year and the end date is prior to the first dose of IP, then assume the end date.

If the month is missing and the year is different from the year of first dose of IP, assume 01-JAN-*YYYY* of the collected year. If the year is the same as the first dose of IP year and the end date is on or after (including ongoing / missing) the first dose of IP, then assume the date of the first dose of IP. If the year is the same as the first dose of IP and the end date is prior to the first dose of IP, then assume the end date.

After applying these rules, if the imputed AE start date is after a complete AE end date then assume the same date as the complete AE end date; if the end date is missing and the imputed AE start date is after the end of study date then assume the same date as the study end date.

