## 3.1.2 Analysis visit windows

For the purpose of the statistical analysis all parameters, except the adverse event, concomitant medication / procedure, medical history, protocol deviations and other non-compliances reported in the CTMS and some demographic data (sex, ethnic group and race) are allocated to the analysis visit as reported in the tables below. The allocation to visit windows is performed after the imputation of date of first and last doses of IP as in section 3.1.1. Measurements with missing or partially missing dates cannot be imputed to any analysis visit.

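### Two SAP safety derivations are wrong as written: undated AEs drop out of every AE summary table, and time from last dose to AE start is calculated from the date of death

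*SAP*

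**What the plan says.** **Undated AEs.** SAP section 3.1.1.4 states: "Only partial AE start dates are imputed; Dates which are completely missing are not imputed". Section 3.3.3.1 then allocates an AE with no start date to a study phase. It is pre-treatment if its end date is known and precedes first dose. If the end date is also missing, or the "AE end date is on or after the first dose of IP date no assignment can be done". The same section treats only on-treatment AEs as treatment-emergent, and section 4.2.6.1 restricts the AE summary tables to that phase. The AE listing in section 4.2.6.1 covers all AEs in the safety analysis set.

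On collection, SAP section 3.3.3.1 says: "All non-serious AEs will be recorded from time of first dose of IP". Protocol section 8.3.1 agrees: "Adverse events will be collected from time of first dose throughout the treatment period and including the follow-up period". SAEs are recorded from consent. SAP Table 5 has two phases, and on-treatment runs from first dose to the end of the study.

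**Time since last dose.** SAP section 4.2.6.1 defines durations for the key-information lists of deaths, SAEs and AEs leading to discontinuation of IP. One formula serves both the interval from last dose to AE start and the interval from last dose to death: date of death, minus date of the last dose before the AE or death, plus 1. In the same list, time from first dose to AE uses the AE start date.

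**The concern.** An AE that belongs in the treatment-emergent tables can be lost from all of them, including the overview count of participants with any AE, only because its start date is blank. The omission works in one direction: it can lower treatment-emergent counts and never raise them. It also sits oddly with the rule for partial dates. If only the year of onset is known, it equals the year of first dose, and the event is not known to have ended earlier, section 3.1.1.4 resolves the doubt towards treatment: "including ongoing / missing) the first dose of IP, then assume the date of the first dose of IP".

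The second formula leaves a listed safety variable without a value for every survivor in the SAE and discontinuation lists. For a fatal case it can give the wrong interval. Time since last dose is part of how each such case is described.

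**Working it through.** The documents give no figure to reproduce here, so the check applies the written rules to test cases. The dosing days (1, 8, 29 and 57) are the planned ones. The event dates are made up.

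**1. Phase allocation under SAP sections 3.1.1.4, 3.3.3.1 and 4.2.6.1**

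| Start date | End date | Phase as written | In summary tables |
|---|---|---|---|
| Missing | 5 days before first dose | Pre-treatment | No (correct) |
| Missing | Day 40 | None | No |
| Missing | Missing (ongoing) | None | No |
| Day 30 | Ongoing | On-treatment | Yes |

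Rows 2 and 3 are the problem. If the event is non-serious, the collection rule puts its recording at or after first dose. Table 5 has only one phase from that point, so the phase is known even though the date is not. If the event is an SAE, it may have begun between consent and first dose, and the phase is undetermined.

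**2. Size of the omission.** Assume equal arms: 108 / 4 = 27 participants. For a participant with no other event in the table row:

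- none omitted: 0 points
- one omitted: 1 / 27 = 3.7 percentage points
- two omitted: 2 / 27 = 7.4 percentage points

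The change is 0 if the participant has another event counted in that row. The documents do not say how many undated AEs to expect. Protocol section 8.3.2 requires "The date and time when the AE started and stopped" for each AE, so a wholly blank start date should be exceptional.

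**3. Time from last dose to AE start.** Take an SAE starting on Day 35, after the Day 29 dose.

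- From AE start: 35 − 29 + 1 = 7 days.
- As written, participant survives: there is no date of death, so no value.
- As written, death on Day 50: 50 − 29 + 1 = 22 days, an excess of 22 − 7 = 15 days.

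In general, with the last dose before the AE used in both terms:

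(death − last dose + 1) − (AE start − last dose + 1) = death − AE start.

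The error is therefore the number of days from AE onset to death, and is zero only if both fall on the same day.

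**The case against.** The strongest reply on the first part is that leaving undated records unassigned is the SAP's general convention. Section 3.1.2 says: "Measurements with missing or partially missing dates cannot be imputed to any analysis visit". For LDL-C, section 3.3.1.1 says: "Measurements with missing or partial missing dates are not assigned to any analysis visit / analysis phase". On this view the SAP declines to classify an event about which nothing is known, and the event stays visible in the listing. The partial-date rule is not a like-for-like comparison, because there the year is known. A collection window also does not strictly prove onset after dosing: the AE definition allows events at any time, and the pre-treatment branches are not limited to SAEs. Moving undated SAEs to on-treatment could count a screening event as treatment-emergent.

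Parts of this stand. The convention is general, the partial-date rule is only an analogy, and for SAEs the current rule leaves the phase open rather than being certainly wrong. It does not rescue the rule for non-serious AEs. An undated laboratory value cannot be placed at any visit, whereas a non-serious AE needs only a phase, and the collection rule supplies it.

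On the second part, the intended formula is fairly plain from the name of the variable and from the neighbouring definition. It is probably a drafting slip, and programming would be likely to expose it. The size given above also depends on taking the last dose before the AE. The SAP wording could be read differently if a dose falls between onset and death. Even so, the formula as written does not produce the variable it names.

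**Conclusion.** Both derivations are wrong as written, and both are minor.

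The first excludes undated non-serious AEs that the plan's own collection rule places on treatment. The number affected is unknown, likely very small and possibly zero. The 3.7 points per omitted participant assumes 27 per arm and no other event from that participant in the row. For SAEs the conclusion is weaker: the phase is unknown, and the SAP should state a convention.

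The second affects only the key-information lists. It gives no value for survivors. For a fatal case it overstates the interval by the days from AE start to death, provided the last dose before the AE is the one subtracted.

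Neither point affects efficacy, sample size or error control, and no AE rate or test depends on the second.

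**What to change.** 1. In SAP section 3.3.3.1, assign an AE with a completely missing start date to the on-treatment phase unless its end date is before first dose. For SAEs, state that this is a conservative convention that may count an event with onset during screening as treatment-emergent, and flag these records in the listing.
2. In SAP section 4.2.6.1, define time from last dose to AE as AE start date minus the date of the last dose before AE start, plus 1. Keep the date-of-death formula for time from last dose to death only.

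The cost is two lines of SAP text and minor programming, with no change to data collection or design.

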### **3.3.3.2 Safety clinical laboratory parameters**

Safety clinical laboratory tests are performed in a central clinical laboratory.

Safety clinical laboratory tests are:

Haematology

- White blood cell (WBC) count
- Red blood cell (RBC) count

- Haemoglobin (Hb)
- Haematocrit (HCT)
- Mean-corpuscular volume (MCV)
- Mean corpuscular haemoglobin concentration (MCHC)
- Neutrophils absolute count
- Lymphocytes absolute count
- Monocytes absolute count
- Eosinophils absolute count
- Basophils absolute count
- Platelets absolute count
- Reticulocytes absolute count

#### Coagulation parameters

- Prothrombin time
- Activated partial thromboplastin time (aPTT)
- International normalized ratio (INR)

#### Clinical chemistry

- Sodium
- Potassium
- Blood urea nitrogen (BUN)
- Creatinine
- Calcium
- Phosphate
- Creatine kinase (CK)
- Direct bilirubin
- alkaline phosphatase (ALP)
- alanine aminotransferase (ALT)
- aspartate aminotransferase (AST)
- gamma glutamyl transferase (GGT)
- Total bilirubin (TBL)
- Glutamate dehydrogenase (GLDH)
- Bicarbonate
- Uric acid
- FSH (women only)
- LH (women only)

#### Urinalysis

- pH (quantitative)
- Specific gravity (quantitative)
- Glucose (qualitative)
- Blood (qualitative)
- Colour (qualitative)
- Protein (qualitative)
- Appearance (qualitative)
- Nitrites (qualitative)
- Ketones (qualitative)
- Leukocytes (qualitative)

- Urobilinogen (qualitative)
- Microscopic panel (if positive for blood, nitrites or protein):
  - Sediment, Leucocytes
  - Sediment, Erythrocytes
  - White Blood Cell Clumps
  - Epithelial Cells, Tubular
  - Epithelial Cells, Squamos
  - Epithelial Cells, Transitional
  - Red Blood Cell Clumps
  - Sediment, Hyaline Casts
  - Sediment, Granular Casts
  - Sediment, Leucocyte Casts
  - Sediment, Erythrocyte Casts
  - Sediment, Epithelial Casts
  - Sediment, Fatty Casts
  - Sediment, Cell casts
  - Broad Casts
  - Sediment, Waxy Casts
  - Sediment, Triple Phosph Cryst.
  - Sediment, Calcium Ox. Cryst.
  - Sediment, Calcium Phosphate
  - Sediment, Calcium carbonate Cryst
  - Sediment, Uric Acid Cryst.
  - Amorphous Crystals
  - Sediment, Leucine Cryst.
  - Sediment, Cystine Cryst.
  - Sediment, Tyrosine Cryst.
  - Sediment, Ammonium Urate Crystals
  - Sediment, Bilirubin Cryst.
  - Sediment, Bacteria
  - Yeast, Budding
  - Sediment, Trichomonas
  - Yeast Hyphae
  - Oval Fat Body
  - Fat
  - Sperm
  - Sediment, Mucus

